11.1 ADVERSE EVENTS

AEs will be coded by SOC and preferred term using the *Medical Dictionary for Regulatory Activities*, version 17.0 or newer.

For patients who completed the lead-in study (VLZ-MD-22), an AE (classified by preferred term) that occurs during the open-label treatment period or during the down-taper period will be considered a treatment-emergent adverse event (TEAE) if it was not present before the date of the first dose of double-blind investigational product in the lead-in study or if it was present before the date of the first dose of double-blind investigational product in the lead-in study and increased in severity during the open-label treatment period or during the down-taper period. If more than 1 AE is reported before the date of the first dose of double-blind investigational product in the lead-in study and coded to the same preferred term, the AE with the greatest severity will be used as the benchmark for comparison with the AEs occurring during the open-label treatment period or during the open-label down-taper period that were also coded to that preferred term. An AE that occurs more than 30 days after the date of the last dose of investigational product will not be counted as a TEAE.

For *de novo* patients, an AE (classified by preferred term) that occurs during the open-label treatment period or during the open-label down-taper period will be considered a TEAE if the AE was not present before the date of the first dose of open-label investigational product or if it was present before the date of the first dose of open-label investigational product and increased in severity during the open-label treatment period or during the open-label down-taper period. If more than 1 AE is reported before the date of the first dose of open-label investigational product and coded to the same preferred term, the AE with the greatest severity will be used as the benchmark for comparison with the AEs occurring during the open-label treatment period or during the open-label down-taper period that were also coded to that preferred term. An AE that occurs more than 30 days after the date of the last dose of investigational product will not be counted as a TEAE.

For patients who completed the lead-in study (VLZ-MD-22), an AE (classified by preferred term) occurring during the open-label treatment period will be considered a newly emergent adverse event (NEAE) if the AE was not present before the first dose of the open-label treatment period investigational product or it was present before the first dose of the open-label treatment period investigational product and increased in severity during the open-label treatment period. If more than 1 AE was reported before the first dose of the open-label investigational product and coded to the same preferred term, the AE with the greatest severity will be used as the benchmark for comparison with the AEs occurring during the open-label treatment period that were also coded to that preferred term.

An AE occurring during the open-label down-taper period will be considered an NEAE if it was not present before the start of the down-taper period or was present before the start of the down-taper period but increased in severity during the down-taper period. An AE that occurs more than 30 days after the date of the last dose of investigational product will not be counted as a NEAE.

The number and percentage of patients reporting TEAEs during the open-label treatment period and during the open-label down-taper period will be tabulated by SOC and preferred term, for both the open-label treatment period and the open-label down-taper period, separately. If more than 1 AE is coded to the same preferred term for the same patient, the patient will be counted only once for that preferred term using the greatest severity and strictest causality for the summarization by severity and by causal relationship to the investigational product, respectively.

The distribution of TEAEs by severity and causal relationship to the investigational product will be summarized separately for the open-label treatment period and the open-label down-taper period.

A common TEAE during the open-label treatment period will be summarized in 2 ways: $\geq 1\%$ of patients and $\geq 2\%$ of patients in any cohort or any lead-in treatment group. The incidence of common TEAEs will be summarized separately by preferred term and cohort and lead-in treatment group and will be sorted by decreasing frequency for the total group.

NEAEs reported during the open-label treatment period and the during open-label down-taper period will be summarized separately by body system and preferred term.

[figure not shown]
A serious adverse event (SAE) that occurred between the date of the first dose of open-label investigational product and 30 days after the date of the last dose of open-label investigational product in the study, inclusive, will be considered an on-therapy SAE. The incidence of SAEs and AEs leading to premature discontinuation of the study will also be summarized by study period, SOC and preferred term. Listings will be presented for patients with SAEs, patients with AEs leading to premature discontinuation, and patients who died (if any). All patients with SAEs, including those reported during the screening period or more than 30 days after the date of the last dose of the open-label investigational product, and patients discontinuing due to AEs before the start of open label investigational product will be included in these listings.

[figure not shown]
Listings will be presented for patients with SAEs, patients with AEs leading to discontinuation, and patients who die (if any).

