The CGI-I ([Guy, 1976](#)) is a clinician rated instrument that will be used to rate total improvement or worsening of mental illness from Baseline (Visit 2), regardless of whether the Investigator considers it to be a result of treatment with the investigational product. The CGI-I will be used to rate the patient's improvement on a scale from 1 to 7, with 1 indicating that the patient is very much improved and 7 indicating the patient is very much worse. A copy of the CGI-I is provided in [Appendix VI](#).

9.5.2 *Safety Assessments*

Patients must be evaluated by a physician or an appropriately trained health care professional at every visit, and the evaluation must be documented. The procedures discussed below will be completed at the designated visits. Safety assessments should not be administered to the patient unless the patient is accompanied by his or her consented caregiver.

9.5.2.1 *Adverse Events*

An AE is any untoward medical occurrence in a patient or clinical investigation patient administered a pharmaceutical product and which does not necessarily have to have a causal relationship with this treatment. An AE can therefore be any unfavorable and unintended sign (including an abnormal laboratory finding, for example), symptom, or disease temporally associated with the use of a medicinal product, whether or not considered related to the medicinal product (ICH-E2A).

For the purpose of the site's data collection responsibilities, any untoward event that is reported from the time the ICF was signed until 30 days after the final protocol-defined study visit or the last known dose of investigational product (if the final visit does not occur) is to be considered an AE.

Examples of AEs are as follows:

- Changes in the general condition of the patient
- Subjective symptoms offered by or elicited from the patient
- Objective signs observed by the Investigator or other study center personnel
- All diseases that occur after signing informed consent, including any change in severity or frequency of preexisting disease
- All clinically relevant abnormalities in laboratory values or clinically relevant physical findings that occur during the study schedule

Particular attention must be given to AEs that were identified in the adult MDD vilazodone program: nausea, vomiting, decreased appetite, and weight loss.

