9.5.2.5 Reporting Adverse Events and Serious Adverse Events

At each visit, patients are to be queried regarding any AEs or SAEs that have occurred since the previous visit. Patients will be asked to volunteer information with a nonleading question such as, "How do you feel since your last visit?" Study center personnel will record all pertinent information in the patient's eCRF.

All AEs must be recorded on the appropriate AE reporting page of the patient's eCRF whether or not they are considered causally related to the investigational product.

For every AE, the Investigator must:

- Provide an assessment of the seriousness of the event (ie, is it an SAE?), as well as the severity and causal relationship
- Document all actions taken with regard to the investigational product
- Detail any other treatment measures taken for the AE
- Document the outcome of the AE

In addition, patients are to be reminded, as described in the ICF and in accordance with Section 9.5.2.1, to notify site personnel of any AEs occurring during the 30-day post-study period. Any AEs reported by the patient (or patient representative) during this period are to be recorded in original source documents. AEs are also to be recorded in the eCRF if at least 1 of the following conditions is met: 1) the event meets the criteria for an SAE (see Sections 9.5.2.4 and 9.5.2.6), and/or 2) the event is judged by the Investigator to be potentially causally related to investigational product.

Any AEs that are ongoing at the time of the final protocol-defined study visit will be followed until the condition returns to prestudy status, has resolved or stabilized, or can be explained as being unrelated to the investigational product. If a follow-up visit is deemed necessary for appropriate safety surveillance, it will take place within 30 days of the final protocol-defined study visit.

9.5.2.6 *Immediate Reporting of Serious Adverse Events and Events of Special Interest*

FRI is required to inform worldwide regulatory authorities of SAEs that meet specific criteria. Therefore, FRI must be notified immediately regarding any SAE that occurs after informed consent is obtained.

Within 24 hours of learning of any AE that meets one of the criteria for an SAE, the study center personnel must report the event to Global Drug Safety on the SAE Form for Clinical Trials. The Study Physician may also be notified by telephone.

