If, during follow-up, any nonserious AE worsens and eventually meets the criteria for an SAE, that AE should be recorded as a new SAE.

The study center must transmit the SAE Form for Clinical Trials to the SAE fax number shown below. Even if an initial report is made by telephone, the SAE Form for Clinical Trials completed with all available details must still be faxed within 24 hours of knowledge of the event at the study center.

Supplemental information should be submitted as soon as available and may include laboratory results, radiology reports, progress notes, hospital admission and emergency room notes, holding and observation notes, discharge summaries, autopsy reports, and death certificates.

The Investigator is expected to take all therapeutic measures necessary for resolution of the SAE. Any medications or procedures necessary for treatment of the SAE must be recorded on the appropriate pages of the patient's eCRF. All SAEs are to be followed by the study staff until resolution or until the SAE is deemed stable. ***FRI may contact the study center to solicit additional information or follow up on the event.***

Fax the SAE Form for Clinical Trials to FRI.

[figure not shown]
United States and Canada: [contact]
Medical Emergency [contact]

[figure not shown]
[figure not shown]
9.5.2.7 *Reporting of Pregnancies Occurring During the Study*

[figure not shown]
Study center personnel must report every pregnancy from the time the ICF was signed until 30 days after the last dose of investigational product. Within 24 hours of learning of the pregnancy, the study center personnel must report the event to FRI Global Drug Safety on the Clinical Trial Pregnancy Form and fax it to the SAE fax number stated in Section 9.5.2.6, even if no AE has occurred. Pregnancies in female partners of male patients occurring during the time frame described above must also be reported.

[figure not shown]
[figure not shown]
Any pregnancy of a patient treated with investigational product must be followed to term and the outcome reported by completing a follow-up Clinical Trial Pregnancy Form. If the pregnancy is associated with an SAE (eg, if the mother is hospitalized for hemorrhage), a separate SAE Form for Clinical Trials must be filed as described in Section 9.5.2.6 with the appropriate serious criterion (eg, hospitalization) indicated in addition to the pregnancy form.

9.5.2.8 *Potential Hy's Law Cases*

**9.5.2.9***Clinical Laboratory Determinations*

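### The emergent-event rules count a pre-existing event only if its severity rises, so one that becomes serious at the same severity is in the SAE table but can be missing from the TEAE or NEAE tables

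*SAP*

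**What the plan says.** **Emergence rules.** SAP 11.1 classifies events by preferred term. An event not seen before the reference date is emergent. One seen before is emergent only if it got more severe:

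- TEAE, de novo patients: "if it was present before the date of the first dose of open-label investigational product and increased in severity during the open-label treatment period"; a rise in the down-taper also counts.
- TEAE, rollover patients: "if it was present before the date of the first dose of double-blind investigational product in the lead-in study and increased in severity" in the open-label treatment or down-taper period.
- NEAE, rollover patients, open-label period (SAP only): "it was present before the first dose of the open-label treatment period investigational product and increased in severity during the open-label treatment period".
- NEAE, down-taper period: the event "was present before the start of the down-taper period but increased in severity during the down-taper period".

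Where a TEAE or open-label NEAE has several earlier records with the same term, "the AE with the greatest severity will be used as the benchmark for comparison". Protocol 9.7.6.1 has the same two TEAE rules and the same down-taper NEAE rule.

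**Seriousness.** Protocol 9.5.2.5 tells the investigator, for every AE, to "Provide an assessment of the seriousness of the event (ie, is it an SAE?), as well as the severity and causal relationship". Under Protocol 9.5.2.6, when a nonserious AE worsens during follow-up and meets an SAE criterion, "that AE should be recorded as a new SAE".

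**SAE reporting.** SAP 11.1 and Protocol 9.7.6.1 define an on-therapy SAE by date alone, from the first open-label dose to 30 days after the last. SAE incidence is tabulated by study period, system organ class and preferred term, and all patients with SAEs are listed.

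**The concern.** The protocol treats becoming serious as a change important enough to need a new record, but the emergence rules do not look at seriousness. A new SAE record does not help, because emergent status depends on whether the preferred term was there before and whether its severity grade rose.

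Vomiting, which Protocol 9.5.2.1 names for particular attention, gives a hypothetical case. A de novo patient has vomiting recorded during screening. On open-label vilazodone it leads to hospitalization, and the investigator keeps the same severity grade. The patient appears under vomiting in the SAE table and not under vomiting in the TEAE table. An event already at the top grade before dosing can never satisfy the rule.

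The study's only objective is long-term safety and tolerability, and its output is descriptive. The TEAE tables are where a reader looks for incidence, severity and attribution to drug. SAEs are planned to be tabulated by period, class and term, with no breakdown by causality. An SAE of this kind that is judged related would therefore be missing from the planned causality summary.

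**Working it through.** The plan gives no figure to reproduce, so the check applies the rules to cases. In each case the event has the same preferred term and severity grade throughout, was nonserious at first, and later becomes serious within the on-therapy SAE window.

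| Case | TEAE? | NEAE for the period in which it becomes serious? | On-therapy SAE? |
|---|---|---|---|
| A. De novo; present before first open-label dose; serious in open-label treatment | No | No such rule for de novo patients | Yes |
| B. Rollover; present before first double-blind dose; serious in open-label treatment | No | No | Yes |
| C. Rollover; first seen after first double-blind dose and before first open-label dose; serious in open-label treatment | Yes | No | Yes |
| D. Either cohort; first seen in open-label treatment; serious in down-taper | Yes | No | Yes |

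Reasoning:

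1. *TEAE.* A and B were present before their reference dates and did not rise in severity, so both routes fail. C and D were absent before the reference date, so they qualify at any severity.
2. *NEAE.* B and C were present before the first open-label dose, and D before the start of the down-taper. None rose in severity.
3. *SAE.* All four fall in the date window, which has no emergence condition.
4. *Severity and causality summaries.* These are summaries of TEAEs, so A and B are missing from them and C and D are not.
5. *Limit of the reading.* If the serious episode is coded to a different preferred term not seen before, it counts as new and the problem does not arise.

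The number of patients affected would be the number of on-therapy SAE patients multiplied by the proportion who had the same term earlier, nonserious and at a severity no lower than that of the serious episode. The documents give neither quantity. The severity scale is not visible in Protocol 9.5.2.3, so how often seriousness changes without a change of grade cannot be judged either.

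**The case against.** The best defence is that nothing serious goes unreported. On-therapy SAEs are tabulated by period and term whether or not they are emergent, AEs leading to discontinuation are handled the same way, and every patient with an SAE is listed. Suicidality has further cover: C-SSRS summaries of the most severe ideation and behavior (SAP 11.5.1) drawn from all postbaseline assessments (SAP 16.4), a listing of AEs in affected patients, and a data monitoring committee (Protocol 9.10). All of this stands. It limits the point to a label and to tables that disagree. It does not remove the disagreement or the omission from the causality summary.

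A reader might infer more in three ways:

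- *That rollovers lose all events carried over from the lead-in.* They do not. An event first seen after the first double-blind dose is still a TEAE in the open-label period (case C); only the NEAE table drops it.
- *That increases in frequency should count too,* because Protocol 9.5.2.1 defines AEs as "including any change in severity or frequency of preexisting disease". That definition governs what sites collect, and an AE definition wider than the emergence rule is not a contradiction. The items Protocol 9.5.2.5 requires are seriousness, severity, causality, action taken, treatment and outcome. The visible text does not show that a change in frequency is recorded, and severity grading may already reflect it.
- *That every SAE after the first open-label dose should be called emergent.* Without an upper limit, that would conflict with the plan's exclusion of events more than 30 days after the last dose.

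**Conclusion.** The gap is real and narrow. A pre-existing event that becomes serious at unchanged severity is counted as an on-therapy SAE. It is left out of the TEAE tables in cases A and B, and out of the relevant NEAE table in cases B, C and D. The emergent-event and SAE tables can then disagree for the same patient and term, and the TEAE severity and causality summaries are incomplete for A and B.

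The documents do not support saying that serious events are lost, that rollovers are the group most exposed in the TEAE table, or that any given share of SAE patients is affected. The number is probably small and cannot be estimated. The conclusion rests on reading the rules as written: comparison by preferred term, with severity as the only measure of worsening. It is a cheap improvement worth making, and it does not threaten the study's safety conclusions.

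**What to change.** In every TEAE and NEAE rule (three in Protocol 9.7.6.1, four in SAP 11.1), change *increased in severity* to *increased in severity or became serious*. Keep the existing limit of 30 days after the last dose. For programming, define *became serious* as a serious record in the period with no serious record of the same preferred term before that rule's reference date. This extends the existing severity benchmark to seriousness. Do not add a frequency criterion unless the case report form is shown to capture frequency change.

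The cost is seven edited clauses and a small change to the derivation. No new data are needed, because seriousness is assessed for every AE. TEAE and NEAE counts may rise slightly.

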8.0 STUDY OBJECTIVE

The objective of this study is to evaluate the long-term safety and tolerability of vilazodone for the treatment of MDD in pediatric outpatients (7-17 years).

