9.3.4 Patient Replacement Procedures

[figure not shown]
Patients who prematurely discontinue treatment will not be replaced.

[figure not shown]

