The study will be approximately 28 weeks in duration, including approximately a 1-week screening/washout period, a 26-week open-label treatment period, and a 1-week down-taper period. During the open-label treatment period, study visits will be conducted after 2, 3, 4, 6, 8, 10, 12, 14, 16, 18, 20, 22, 24, and 26 weeks of treatment (see [Table 4-1](#)). Safety and efficacy assessments will be performed at the designated visits. Patients prematurely discontinuing from the study, regardless of cause, will be seen for a final evaluation.

This statistical analysis plan (SAP) provides a more technical and detailed elaboration of the statistical analyses for efficacy and safety assessments as outlined and/or specified in the final study protocol (version dated 15 Dec 2014). Specifications of tables, figures, and data listings are contained in a separate document.

Table 4–1. SCHEDULE OF EVALUATIONS: Study VLZ-MD-23

Table 4-1.

SCHEDULE OF EVALUATIONS: Study VLZ-MD-23

The table content is completely obscured by a large black rectangular redaction box.

5.0**OBJECTIVE**

The objective of this study is to evaluate the long-term safety and tolerability of vilazodone for the treatment of MDD in pediatric outpatients (7-17 years).

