6.3 SAFETY POPULATION

The Safety Population will consist of all patients who took at least 1 dose of open-label investigational product.

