6.4 INTENT-TO-TREAT POPULATION

The Intent-to-Treat (ITT) Population will consist of all patients in the Safety Population who had a baseline and at least 1 postbaseline assessment of the Children's Depression Rating Scale-Revised (CDRS-R) total score.

7.0

PATIENT DISPOSITION

The number of patients in the Screened Population will be summarized overall by study center. The number of patients in the Enrolled, Safety, and ITT populations will be summarized by study center.

Screen failures (ie, patients who were screened but not included in the Enrolled Population) and the associated reasons for failure will be tabulated. The number and percentage of patients who complete the open-label treatment period and of patients who prematurely discontinue during the same period will be presented. The reasons for premature discontinuation from the open-label treatment period as recorded on the disposition pages of the electronic case report forms will be summarized (number and percentage) for the Safety Population. All patients who prematurely discontinue during the open-label treatment period will be listed by discontinuation reason for the Safety Population.

All summaries in this section will be presented by patient cohort (rollover patients from Study VLZ-MD-22 or *de novo* patients) and overall. The rollover patients from Study VLZ-MD-22 will be summarized by lead-in treatment group.

8.0

DEMOGRAPHICS AND OTHER BASELINE CHARACTERISTICS

[figure not shown]
Demographic parameters (age, sex, race, ethnicity) and other baseline characteristics (weight, height, body mass index) will be summarized descriptively by cohort and by lead-in treatment group for the Safety and ITT populations, respectively. Baseline efficacy variables will be summarized by cohort and by lead-in treatment group for the ITT Population.

Continuous variables will be summarized by number of patients and mean, SD, median, minimum, and maximum values. Categorical variables will be summarized by number and percentage of patients.

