Medical and surgical history/physical findings will be classified by system organ class (SOC) and preferred term using the *Medical Dictionary for Regulatory Activities*, version 17.0 or newer. The number and percentage of patients with abnormalities in medical and surgical histories in each SOC and preferred term will be summarized by cohort and by lead-in treatment group for the Safety Population. Psychiatric history of MDD, other psychiatric history, prior treatment with psychotropic medication, and non-drug psychiatric treatment history will also be summarized by cohort and by lead-in treatment group for the Safety Population.

[figure not shown]
The *World Health Organization Drug Dictionary*, version March 2014 or newer, will be used to classify prior and concomitant medications by therapeutic class and drug name.

Prior medication is defined as any recorded medication taken before the date of the first dose of open-label investigational product. *Concomitant medication* is defined as any medication taken on or after the date of the first dose of open-label investigational product.

9.0**EXTENT OF EXPOSURE AND TREATMENT COMPLIANCE****9.1****EXTENT OF EXPOSURE**

Exposure to open-label investigational product for the Safety Population during the open-label treatment period will be summarized in terms of treatment duration, calculated as the number of days from the date of the first dose of open-label investigational product to taken the date of the last dose of open-label investigational product taken during the open-label treatment period, inclusive. Descriptive statistics (number of patients, mean, SD, median, minimum, and maximum) will be presented by cohort and by lead-in treatment group. The number and percentage of patients by exposure will be presented for specific intervals by cohort.

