11.0 SAFETY ANALYSES

The safety analysis will be performed for the open-label treatment period and down-taper period separately using the Safety Population. The safety analyses will be presented by patient cohort (rollover patients from Study VLZ-MD-22 and *de novo* patients) and overall. The rollover patients from Study VLZ-MD-22 will also be presented by lead-in treatment group.

The safety parameters will include adverse events (AEs), clinical laboratory parameters, vital sign measurements, electrocardiogram (ECG) parameters, Columbia Suicide Severity Rating Scale (C-SSRS) evaluations, and the change from baseline in the age- and gender-adjusted height (evaluation of growth). For patients who completed the lead-in study (VLZ-MD-22), the baseline for safety parameters from the lead-in study will be used as the baseline for this study. For *de novo* patients, the latest nonmissing evaluation of safety parameters before the first dose of open-label investigational product will be used as the baseline.

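### In the visible text, adverse events are summarised only as crude percentages of everyone dosed; with unequal time at risk these understate 26-week on-treatment risk, most for late-onset events

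*SAP*

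**What the plan says.** The only objective is "to evaluate the long-term safety and tolerability of vilazodone" (Protocol 8.0), over "a 26-week open-label treatment period" (SAP 4.0).

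- **Analysis set.** SAP 11.0: "The safety analysis will be performed for the open-label treatment period and down-taper period separately using the Safety Population". SAP 6.3: "The Safety Population will consist of all patients who took at least 1 dose of open-label investigational product". There is no minimum time on drug.
- **Measure.** SAP 11.1 gives "The number and percentage of patients reporting TEAEs during the open-label treatment period", by system organ class and preferred term. Serious events and events leading to discontinuation are given as incidence by study period. SAP 11.5.1 gives C-SSRS ideation and behaviour as counts and percentages. Protocol 9.7.6.1 and 9.7.6.5.1 match this.
- **Counting limit.** Events more than 30 days after the last dose are not treatment-emergent (SAP 11.1).
- **Exposure.** SAP 9.1 derives each patient's days on open-label drug, and "The number and percentage of patients by exposure will be presented for specific intervals by cohort". The visible safety sections do not use these days.
- **Leaving early.** Under Protocol 9.4.10, patients whose depression worsens or is inadequately controlled and who stop the drug, and those who need another treatment, leave the study. SAP 7.0 says the number and percentage "of patients who prematurely discontinue during the same period will be presented". Neither document states an expected rate.

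**The concern.** A patient who stops at Week 3 stays in the denominator of a 26-week table but can contribute only events seen up to the stop and shortly after it. The more patients leave, and the later an event tends to arise, the further the crude percentage falls below the risk for a patient who stays on drug for 26 weeks. Late events are what a long-term study is best placed to show.

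Two readings are at stake. A low percentage for a late event could mean low risk or few children left at risk, and the table cannot tell these apart. The rollover and de novo columns also become hard to compare if retention differs. It may well differ, since rollover patients have all completed a previous study.

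**Working it through.** There is no figure in the plan to reproduce: the visible text gives no event rate, dropout rate or precision target.

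**Inputs from the documents:** denominator, all dosed (SAP 6.3, 11.0); horizon, 26 weeks (SAP 4.0); post-dose window, 30 days (SAP 11.1); planned N, about 250 (SAP 14.0) or about 315 (Protocol 9.1.2).

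**Assumed:** dropout D by Week 26 of 20%, 35% or 50%, at a constant rate and unrelated to the event; true 26-week risk p of 10%.

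**1. Constant hazard.** With l = -ln(1-p)/26 and d = -ln(1-D)/26, the expected crude proportion is l/(l+d) × [1 - (1-p)(1-D)].

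- D = 20%: 0.10536/(0.10536 + 0.22314) × (1 - 0.9×0.80) = 0.3207 × 0.28 = 8.98%
- D = 35%: 0.10536/(0.10536 + 0.43078) × (1 - 0.9×0.65) = 0.1965 × 0.415 = 8.16%
- D = 50%: 0.10536/(0.10536 + 0.69315) × (1 - 0.9×0.50) = 0.1319 × 0.55 = 7.26%

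**2. Onset confined to Weeks a to b.** The ratio is close to the mean fraction still on treatment in that window: [(1-D)^(a/26) - (1-D)^(b/26)] / [-ln(1-D) × (b-a)/26].

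- Weeks 13-26: D = 20%, (0.8944 - 0.8000)/0.1116 = 0.85; D = 35%, (0.8062 - 0.6500)/0.2154 = 0.73; D = 50%, (0.7071 - 0.5000)/0.3466 = 0.60
- Weeks 0-4: D = 20%, (1 - 0.9663)/0.0343 = 0.98; D = 35%, (1 - 0.9359)/0.0663 = 0.97; D = 50%, (1 - 0.8989)/0.1066 = 0.95

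| Crude / true | D = 20% | D = 35% | D = 50% |
|---|---|---|---|
| Onset Weeks 0-4 | 0.98 | 0.97 | 0.95 |
| Constant hazard (p = 10%) | 0.90 | 0.82 | 0.73 |
| Onset Weeks 13-26 | 0.85 | 0.73 | 0.60 |

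**3. Effect of the 30-day window.** Suppose every event within 30 days of the last dose were captured at an unchanged hazard. With p = 5% and D = 30%, the crude figure moves from 4.21% to 4.44% (constant hazard), from 3.83% to 4.07% (Weeks 13-26) and from 3.65% to 3.87% (Weeks 20-26). For Weeks 0-4 it moves from 4.87% to 5.00%. This is close to a best case: after the final visit, Protocol 9.5.2.5 puts only serious or possibly related events in the eCRF.

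**4. Would the alternatives recover the risk?** Simulation used 4,000 replicates, N = 250 and 315, p = 5%, D = 30%, and early (Weeks 0-4), constant or late (Weeks 20-26) onset. The mean Kaplan-Meier estimate at Week 26 was 5.0% in all three patterns (SD 1.3 to 1.6 points). The mean crude percentage was about 4.9%, 4.2% and 3.7%. First events per 100 patient-years averaged about 12.3, 10.3 and 8.8. For constant hazard this agrees with 0.05129/26 × 52.18 × 100 = 10.3. The same true risk gives different rates when the hazard is not constant, so the rate alone is not enough.

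**5. Two consequences.** If one cohort lost 20% and the other 50%, an identical 10% risk would appear as 9.0% and 7.3% (step 1). At 30% dropout, a Weeks 20-26 event with a true risk of 2.7% would appear as 1.97%. That is just under the SAP's 2% cut for common events, though still above its 1% cut.

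**The case against.** The strongest reply is that the plan never names 26-week cumulative incidence under continued treatment as its target. The study is descriptive, and the crude percentage is a valid estimate of the proportion of dosed patients with an event observed before stopping or within the window. That stands. The crude table is not wrong; it is incomplete for a long-term safety objective.

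Much context is also reported: discontinuation reasons by cohort, exposure intervals, and listings of serious events and of C-SSRS results by visit. A reader can therefore see unequal retention, but cannot turn it into a risk by Week 26.

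Three stronger readings are tempting and not supported:

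- A reader might blame the rule that "Patients who prematurely discontinue treatment will not be replaced" (Protocol 9.3.4). It is not the cause. A replaced patient who had been dosed would stay in the denominator with the same short follow-up. The cause is unequal time at risk.
- A reader might infer that an early leaver is counted as free of events for all 26 weeks. Events before exit count, and so may events in the following 30 days.
- A reader might infer that no time-adjusted analysis exists anywhere. Parts of the SAP are not shown and table specifications are in a separate document, so the absence can be asserted only for the visible text.

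Two technical objections also stand. If dropout is related to the event, Kaplan-Meier is biased too. For adverse events leading to discontinuation, stopping for another reason is a competing event, and one minus Kaplan-Meier would overstate the proportion who stop for an adverse event.

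**Conclusion.** The point holds as a cheap improvement, not as an error that invalidates the tables. On the visible text, adverse events, serious events, discontinuation events and C-SSRS events have no summary that accounts for time at risk. Relative to the 26-week on-treatment risk, the crude percentage is low by about 10% to 27% for a constant hazard (true risk 10%), 15% to 40% for onset in Weeks 13-26 and 2% to 5% for onset in Weeks 0-4, before the partial offset from the 30-day window.

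These sizes rest on assumed dropout of 20% to 50% at a constant rate and unrelated to the event. The documents supply no rate, so the true size is unknown. It would be small if retention is good or events arise early.

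**What to change.** Keep the crude tables. In SAP 11.1 and 11.5.1 add, for the open-label period, by cohort and overall:

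1. Patients with a first event per patient-year at risk, for common treatment-emergent events, serious events, adverse events leading to discontinuation and suicidality events. Person-time should run from the first open-label dose to the first event or the end of risk, with the end of risk stated.
2. A descriptive Week-26 Kaplan-Meier estimate with numbers at risk, for common treatment-emergent events, serious events and suicidality events. Include a sentence that dropout may be informative.
3. For adverse events leading to discontinuation, a cumulative incidence function at Week 26 with other discontinuation as the competing event, in place of one minus Kaplan-Meier.

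If the separate table specifications already contain these, a cross-reference in the SAP is enough.

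The cost is a short SAP paragraph and a few tables, built from dosing, event and visit dates that the plan already needs. No new data are required, and descriptive estimates fit a plan without inference. The downside is that some reported incidences will look less favourable than the crude ones.
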